14.1.2.4.3 Determination of non-target lesion response

Table 14-2 Response criteria for non-target lesions

Response Criteria	Evaluation of non-target lesions
Complete Response (CR):	Disappearance of all non-target lesions. In addition, all lymph nodes assigned a non-target lesions must be non-pathological in size (< 10 mm short axis)
Progressive Disease (PD):	Unequivocal progression of existing non-target lesions. ¹
Non-CR/Non-PD:	Neither CR nor PD
Unknown (UNK)	Progression has not been documented and one or more non-target lesions have not been assessed or have been assessed using a different method than baseline.

¹. Although a clear progression of non-target lesions only is exceptional, in such circumstances, the opinion of the treating physician does prevail and the progression status should be confirmed later on by the review panel (or study chair).

Notes on non-target lesion response

- The response for non-target lesions is **CR** only if all non-target non-nodal lesions which were evaluated at baseline are now all absent and with all non-target nodal lesions returned to normal size (i.e. < 10 mm). If any of the non-target lesions are still present, or there are any abnormal nodal lesions (i.e. ≥ 10 mm) the response can only be ‘**Non-CR/Non-PD**’ unless any of the lesions was not assessed (in which case response is **UNK**) or there is unequivocal progression of the non-target lesions (in which case response is **PD**).
- **Unequivocal progression:** To achieve “unequivocal progression” on the basis of non-target disease there must be an overall level of substantial worsening in non-target disease

such that, even in presence of CR, PR or SD in target disease, the overall tumor burden has increased sufficiently to merit discontinuation of therapy. A modest “increase” in the size of one or more non-target lesions is usually not sufficient to qualify for unequivocal progression status. The designation of overall progression solely on the basis of change in non-target disease in the face of CR, PR or SD of target disease is therefore expected to be rare. In order for a PD to be assigned on the basis of non-target lesions, the increase in the extent of the disease must be substantial even in cases where there is no measurable disease at baseline. If there is unequivocal progression of non-target lesion(s), then at least one of the non-target lesions must be assigned a status of “Worsened”. Where possible, similar rules to those described in [Section 14.1.2.4.2](#) for assigning PD following a CR for the non-target lesion response in the presence of non-target lesions nodal lesions should be applied.

14.1.2.4.4 New lesions

The appearance of a new lesion is always associated with Progressive Disease (PD) and has to be recorded as a new lesion in the New Lesion CRF page.

- If a new lesion is **equivocal**, for example because of its small size, continued therapy and follow-up evaluation will clarify if it represents truly new disease. If repeat scans confirm there is definitely a new lesion, then progression should be declared using the date of the first observation of the lesion
- If new disease is observed in a region which was **not scanned at baseline** or where the particular baseline scan is not available for some reason, then this should be considered as a PD. The one exception to this is when there are no baseline scans at all available for a patient in which case the response should be UNK, as for any of this patient's assessment (see [Section 14.1.2.5](#)).
- A **lymph node is considered as a “new lesion”** and, therefore, indicative of progressive disease if the short axis increases in size to ≥ 10 mm for the first time in the study plus 5 mm absolute increase.

FDG-PET: can complement CT scans in assessing progression (particularly possible for ‘new’ disease). See [Section 14.1.2.2](#).

14.1.2.5 Evaluation of overall lesion response

The evaluation of overall lesion response at each assessment is a composite of the target lesion response, non-target lesion response and presence of new lesions as shown below in [Table 14-3](#).

Table 14-3 Overall lesion response at each assessment

Target lesions	Non-target lesions	New Lesions	Overall lesion response
CR	CR	No	CR ¹
CR	Non-CR/Non-PD ³	No	PR
CR, PR, SD	UNK	No	UNK
PR	Non-PD and not UNK	No	PR ¹
SD	Non-PD and not UNK	No	SD ^{1,2}
UNK	Non-PD or UNK	No	UNK ¹

PD	Any	Yes or No	PD
Any	PD	Yes or No	PD
Any	Any	Yes	PD

¹. This overall lesion response also applies when there are no non-target lesions identified at baseline.

². Once confirmed PR was achieved, all these assessments are considered PR.

³. As defined in [Section 14.1.2.4](#)

If there are no baseline scans available at all, then the overall lesion response at each assessment should be considered Unknown (UNK).

If the evaluation of any of the target or non-target lesions identified at baseline could not be made during follow-up, the overall status must be ‘unknown’ unless progression was seen.

In some circumstances it may be difficult to distinguish residual disease from normal tissue. When the evaluation of complete response depends on this determination, it is recommended that the residual lesion be investigated (fine needle aspirate/biopsy) to confirm the CR.

14.1.3 Efficacy definitions

The following definitions primarily relate to patients who have measurable disease at baseline. [Section 14.1.3.2.8](#) outlines the special considerations that need to be given to patients with no measurable disease at baseline in order to apply the same concepts.

14.1.3.1 Best overall response

The best overall response is the best response recorded from the start of the treatment until disease progression/recurrence (taking as reference for PD the smallest measurements recorded since the treatment started). In general, the patient's best response assignment will depend on the achievement of both measurement and confirmation criteria.

The best overall response will usually be determined from response assessments undertaken while on treatment. However, if any assessments occur after treatment withdrawal the protocol should specifically describe if these will be included in the determination of best overall response and/or whether these additional assessments will be required for sensitivity or supportive analyses. As a default, any assessments taken more than 30 days after the last dose of study treatment will not be included in the best overall response derivation. If any alternative cancer therapy is taken while on study any subsequent assessments would ordinarily be excluded from the best overall response determination. If response assessments taken after withdrawal from study treatment and/or alternative therapy are to be included in the main endpoint determination, then this should be described and justified in the protocol.

Where a study requires confirmation of response (PR or CR), changes in tumor measurements must be confirmed by repeat assessments that should be performed not less than 4 weeks after the criteria for response are first met.

Longer intervals may also be appropriate. However, this must be clearly stated in the protocol. The main goal of confirmation of objective response is to avoid overestimating the response rate observed. In cases where confirmation of response is not feasible, it should be made clear when reporting the outcome of such studies that the responses are not confirmed.

- For non-randomized trials where response is the primary endpoint, confirmation is needed.

- For trials intended to support accelerated approval, confirmation is needed
- For all other trials, confirmation of response may be considered optional.

The best overall response for each patient is determined from the sequence of overall (lesion) responses according to the following rules:

- CR = at least two determinations of CR at least 4 weeks apart before progression where confirmation required or one determination of CR prior to progression where confirmation not required
- PR = at least two determinations of PR or better at least 4 weeks apart before progression (and not qualifying for a CR) where confirmation required or one determination of PR prior to progression where confirmation not required
- SD = at least one SD assessment (or better) > 6 weeks after randomization/start of treatment (and not qualifying for CR or PR).
- PD = progression ≤ 12 weeks after randomization/ start of treatment (and not qualifying for CR, PR or SD).
- UNK = all other cases (i.e. not qualifying for confirmed CR or PR and without SD after more than 6 weeks or early progression within the first 12 weeks)

Overall lesion responses of CR must stay the same until progression sets in, with the exception of a UNK status. A patient who had a CR cannot subsequently have a lower status other than a PD, e.g. PR or SD, as this would imply a progression based on one or more lesions reappearing, in which case the status would become a PD.

Once an overall lesion response of PR is observed (which may have to be a confirmed PR depending on the study) this assignment must stay the same or improve over time until progression sets in, with the exception of an UNK status. However, in studies where confirmation of response is required, if a patient has a single PR (≥30% reduction of tumor burden compared to baseline) at one assessment, followed by a <30% reduction from baseline at the next assessment (but not ≥20% increase from previous smallest sum), the objective status at that assessment should be SD. Once a confirmed PR was seen, the overall lesion response should be considered PR (or UNK) until progression is documented or the lesions totally disappear in which case a CR assignment is applicable. In studies where confirmation of response is not required after a single PR the overall lesion response should still be considered PR (or UNK) until progression is documented or the lesion totally disappears in which case a CR assignment is applicable.

Example: In a case where confirmation of response is required the sum of lesion diameters is 200 mm at baseline and then 140 mm - 150 mm - 140 mm - 160 mm - 160 mm at the subsequent visits. Assuming that non-target lesions did not progress, the overall lesion response would be PR - SD - PR - PR - PR. The second assessment with 140 mm confirms the PR for this patient. All subsequent assessments are considered PR even if tumor measurements decrease only by 20% compared to baseline (200 mm to 160 mm) at the following assessments.

If the patient progressed but continues study treatment, further assessments are not considered for the determination of best overall response.

Note: these cases may be described as a separate finding in the CSR but not included in the overall response or disease control rates.

The best overall response for a patient is always calculated, based on the sequence of overall lesion responses. However, the overall lesion response at a given assessment may be provided from different sources:

- Investigator overall lesion response
- Central Blinded Review overall lesion response
- Novartis calculated overall lesion response (based on measurements from either Investigator or Central Review)

The primary analysis of the best overall response will be based on the sequence of investigator overall lesion responses.

Based on the patients' best overall response during the study, the following rates are then calculated:

Overall response rate (ORR) is the proportion of patients with a best overall response of CR or PR. This is also referred to as 'Objective response rate' in some protocols or publications.

Disease control rate (DCR) is the proportion of patients with a best overall response of CR or PR or SD.

Another approach is to summarize the progression rate at a certain time point after baseline. In this case, the following definition is used:

Early progression rate (EPR) is the proportion of patients with progressive disease within 8 weeks of the start of treatment.

The protocol should define populations for which these will be calculated. The timepoint for EPR is study specific. EPR is used for the multinomial designs of [Dent and Zee \(2001\)](#) and counts all patients who at the specified assessment (in this example the assessment would be at 8 weeks \pm window) do not have an overall lesion response of SD, PR or CR. Patients with an unknown (UNK) assessment at that time point and no PD before, will not be counted as early progressors in the analysis but may be included in the denominator of the EPR rate, depending on the analysis population used. Similarly when examining overall response and disease control, patients with a best overall response assessment of unknown (UNK) will not be regarded as "responders" but may be included in the denominator for ORR and DCR calculation depending on the analysis population (e.g. populations based on an ITT approach).

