7.1 Study flow and visit schedule

[Table 7-1](#) lists all of the assessments and indicates with an “X”, the visits when they are performed. All data obtained from these assessments must be supported in the patient’s source documentation. The table (“Category” column) indicates which assessments produce data to be entered into the clinical database (D) or remain in source documents only (S).

No CRF will be used as a source document.

Screening/baseline evaluations must be performed ≤ 21 days before Cycle 1 Day 1, except for baseline radiological evaluations which must be done within 28 days. Assessments performed as part of the screening evaluations and within 3 days prior to the first dose of study treatment, are not required to be repeated on the first dosing day.

Laboratory and radiological assessments performed as part of standard of care prior to signing informed consent may be used if performed within 21 days and 28 days respectively, of Cycle 1 Day 1.

During the course of the study visits, test and/or procedures should occur on schedule whenever possible. A visit window of ± 7 days is allowed. If the infusion of MCS110 and/or PDR001 is delayed, the visits assessments will be shifted accordingly. On PK collection days the windows are provided in [Section 7.2.3](#).

Radiological assessments must be performed ± 1 week of the scheduled date of the assessment.

For Japan only, patients are required to be hospitalized during Cycle 1.

Visit name	Category	Protocol Section	Screening Phase	Treatment Phase														Follow-up	Disease Progression F/U	Survival F/U	
			Screening	Cycle 1					Cycle 2		Cycle 3	Cycle 4					Subsequent cycles	EOT			Safety F/U
Day of cycle			-21 to -1	1	2	4	8	15	1	15	1	1	2	4	8	15	1				
Prior/concomitant medications, surgery and medical procedures	D	7.1.1.2 7.1.5 and 6.4	X	Continuous ¹																	
Physical examination	S	7.2.2.1	X	X			X	X	X	X	X	X					X	X			
Height	D	7.2.2.3	X																		
Weight	D	7.2.2.3	X	X					X		X	X					X	X			
Vital signs	D	7.2.2.2	X	X			X	X	X	X	X	X					X	X			
Performance status	D	7.2.2.4	X	X					X		X	X					X	X			
Hematology	D	7.2.2.5.1	X	X			X	X	X	X	X	X			X		X	X			
Chemistry	D	7.2.2.5.2	X	X			X	X	X	X	X	X			X		X	X			
Coagulation	D	7.2.2.5.6	X	Only if clinically significant														X			
Urinalysis	D	7.2.2.5.3	X	X					X		X	X					X	X			
Thyroid function	D	7.2.2.5.4	X	X					X		X	X					X	X			

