7.1.2 Treatment period

A treatment cycle is defined as 21 days for the purposes of scheduling procedures and evaluations. Please refer to [Table 7-1](#) for details of the timing of required assessments and [Section 7.1](#) for visit windows.

Patients will be treated until they experience unacceptable toxicity, progressive disease per irRC and/or treatment is discontinued at the discretion of the investigator or the patient, as described in [Section 7.1.3](#) and [Section 4.3](#).

Patients should not discontinue treatment based on progressive disease per RECIST v1.1.

Accumulating evidence indicates that objective responses to immunotherapy follows delayed kinetics of weeks or months, and can be preceded by initial apparent radiological progression or appearance of new lesions or some enlarging lesions while other target lesions are regressing (“mixed response”) ([Wolchok 2009](#)). It is therefore reasonable to allow for these possibilities and continue to treat the patient until progression is confirmed and found to be advancing at the next imaging assessment as per irRC. An outline of the irRC is provided in [Appendix 2](#).

These considerations should be balanced by clinical judgment as to whether the patient is clinically deteriorating and unlikely to receive any benefit from continued treatment.

Such deterioration will be assessed to have occurred after a clinical event that, in the Investigator's opinion, is attributable to disease progression, is unlikely to reverse with continued study treatment and therefore indicates that the patient is not benefiting from study treatment and cannot be managed by the addition of supportive care.

The decision to continue or stop treatment should be discussed with the Novartis Medical Responsible and will be documented in the study files.

The following criteria should be considered for treatment continuation decision making:

- Patients with partial response or stable disease as well as patients with unconfirmed progressive disease (per irRC) should continue to receive study treatment until the next cycle.

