7.2 Assessment types

7.2.1 Efficacy assessments

Tumor response will be determined locally according to two sets of criteria:

1. RECIST v1.1 ([Appendix 1](#))
2. irRC ([Appendix 2](#))

The local investigator's assessment will be used for the analysis of response according to both RECIST v1.1 and irRC, and for treatment decision making (study discontinuation due to PD is per irRC). During the course of the study, Novartis may decide to have a central review of the radiological assessments performed. In such case, the investigator's staff will be instructed on how to send data from these radiological assessments to a Contract Research Organization (CRO) for central review when needed.

At screening, all patients will undergo CT with i.v. contrast of the chest, abdomen and pelvis. If there is clinical evidence of disease in the neck, a CT with i.v. contrast of the neck will also

be performed. MRI should only be used to evaluate sites of disease that are not adequately imaged by CT. If a patient is intolerant of iodine-based contrast agents, CTs may be performed without contrast. MRI may be used to evaluate sites of disease where a CT without i.v. contrast is not adequate. Visible skin lesions and easily palpable subcutaneous tumors may be measured by physical examination using a ruler or calipers. Ultrasound should not be used to measure sites of disease. See [Table 7-2](#) for further details.

Tumor assessments will be performed at the following time points until progression of disease per irRC or patient withdrawal:

- Screening
- Every 2 cycles from Cycle 3 Day 1 up to Cycle 9 Day 1, then every 3 cycles until Cycle 18 Day 1 (1 year of treatment). Assessment will be performed every 4 cycles thereafter, starting from Cycle 22 Day 1.
- At the End of Treatment, if a scan was not conducted within 30 days prior to End of Treatment
- After EOT, during disease progression follow-up, every 9 weeks (\pm 1 week) until week 51, then every 12 weeks (\pm 1 week), until progression of disease per irRC.
- PR or CR, per both RECIST v1.1 and irRC, will be confirmed by a new assessment after at least 4 weeks. Also Progressive Disease (PD), as per irRC, will be confirmed after at least 4 weeks.

If available, tumor markers collected as per local guidelines will be collected at the same time as RECIST tumor evaluation.

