Efficacy assessments should be performed \pm 1 week from the calculated study day as described in [Section 7.1](#). Disease progression follow-up should be performed as described in [Section 7.1.5](#).

Table 7-2 Disease assessment collection plan

Procedure	Screening/Baseline	During Treatment/Follow-up
Chest, abdomen and pelvis CT or MRI (with intravenous contrast enhancement)	Mandated	
 • Every 6 weeks until end of cycle 8 (C3D1, C5D1, C7D1, C9D1) • Thereafter every 9 weeks (C12D1, C15D1, C18D1). • During year two, assessment can be performed every 4 cycles, starting from C22D1. • End of treatment, if not conducted within 30 days prior to EOT.
Tumor markers	If available as per local guideline	Same time as CT or MRI tumor assessment, if available as per local guideline
Brain CT or MRI	If clinically indicated	If lesions were documented at baseline, follow same schedule as CT/MRI of chest, abdomen, and pelvis
Localized bone CT, MRI or x-ray of other metastatic sites (eg neck or bone)	For any lesions already identified that are not visible on the chest, abdomen and pelvis CT or MRI	If lesions were documented at baseline, follow same schedule as CT/MRI of chest, abdomen, and pelvis

Procedure	Screening/Baseline	During Treatment/Follow-up
Color photography (with scale/ruler)	For any skin lesions present	If lesions were documented at baseline, follow same schedule as CT/MRI of chest, abdomen, and pelvis

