14.1.3.2.7 Definition of start and end dates for time to event variables

Assessment date

For each assessment (i.e. evaluation number), the **assessment date** is calculated as the latest of all measurement dates (e.g. X-ray, CT-scan) if the overall lesion response at that assessment is CR/PR/SD/UNK. Otherwise - if overall lesion response is progression - the assessment date is calculated as the earliest date of all measurement dates at that evaluation number.

Start dates

For all “time to event” variables, other than duration of response, the randomization/ date of treatment start will be used as the start date.

For the calculation of duration of response the following start date should be used:

- Date of first documented response is the assessment date of the first overall lesion response of CR (for duration of overall complete response) or CR / PR (for duration of overall response) respectively, when this status is later confirmed.

End dates

The end dates which are used to calculate ‘time to event’ variables are defined as follows:

- Date of death (during treatment as recorded on the treatment completion page or during follow-up as recorded on the study evaluation completion page or the survival follow-up page).
- Date of progression is the first assessment date at which the overall lesion response was recorded as progressive disease.
- Date of last adequate tumor assessment is the date the last tumor assessment with overall lesion response of CR, PR or SD which was made before an event or a censoring reason occurred. In this case the last tumor evaluation date at that assessment is used. If no post-baseline assessments are available (before an event or a censoring reason occurred) the date of randomization/start of treatment is used.
- Date of next scheduled assessment is the date of the last adequate tumor assessment plus the protocol specified time interval for assessments. This date may be used if back-dating

is considered when the event occurred beyond the acceptable time window for the next tumor assessment as per protocol (see [Section 14.1.3.2.8](#)).

Example (if protocol defined schedule of assessments is 3 months): tumor assessments at baseline - 3 months - 6 months - missing - missing - PD. Date of next scheduled assessment would then correspond to 9 months.

- Date of discontinuation is the date of the end of treatment visit.

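### The RECIST v1.1 minimum for stable disease (more than 6 weeks) falls at the centre of the first scan's ±1 week window, so SD seen only on a compliant early scan drops out of DCR

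*Protocol*

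**What the plan says.** Protocol Appendix 1, section 14.1.3.1, defines best overall response (BOR) of SD as "SD = at least one SD assessment (or better) > 6 weeks after randomization/start of treatment", for patients who do not qualify for CR or PR. BOR is PD if progression occurs by 12 weeks and no better category applies. Everything else is unknown (UNK). In the same section, DCR "is the proportion of patients with a best overall response of CR or PR or SD". Section 14.1.3.1 does not count UNK patients as responders but may keep them in the denominator.

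On timing, Protocol 7.1.2 says: "A treatment cycle is defined as 21 days for the purposes of scheduling procedures and evaluations". Protocol 7.2.1 schedules scans "Every 2 cycles from Cycle 3 Day 1 up to Cycle 9 Day 1", and Table 7-2 describes this interval as six-weekly. Protocol 7.1 adds the window: "Radiological assessments must be performed ± 1 week of the scheduled date of the assessment".

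DCR per RECIST v1.1 is a secondary endpoint in both parts (Protocol Table 3-1; SAP 2.7.1). It is summarised with a 90% confidence interval, and BOR is tabulated (SAP 2.7.2). The SAP does not restate or adapt the SD minimum.

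**The concern.** A minimum duration for SD is normal. The difficulty is where this one sits. It coincides with the due date of the first scan, so it splits the compliant window. Two patients with the same disease course, both scanned according to protocol, can receive different BOR categories because one was scanned a few days before the due date.

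What is at stake is the RECIST v1.1 DCR and the BOR table. In a group of about 20, one reclassified patient moves DCR by 1/20 = 5 points.

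A related gap is that section 14.1.3.1 does not say how days are counted for either the 6-week or the 12-week limit, and scheduled scans fall exactly on both.

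**Working it through.** Below, "day n" means n days after first dose. SAP study day is n + 1 (SAP 2.1.1).

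**1. Calendar.** C3D1 = 2 × 21 = day 42 = 6.0 weeks (study day 43), which reproduces the six-weekly interval in Table 7-2. C5D1 = 4 × 21 = day 84 = 12.0 weeks (study day 85). With ±7 days, the first scan is compliant on days 35-49 and the second on days 77-91.

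**2. Which first-scan days satisfy the SD rule (15 compliant days).**

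| Day count | Qualify | Do not qualify |
|---|---|---|
| SAP study day (+1) | days 42-49 (8) | days 35-41 (7) |
| Plain elapsed days | days 43-49 (7) | days 35-42 (8) |

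Days 35-41 fail under either count. The on-schedule scan qualifies under the SAP count.

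**3. Where the patient goes.** Take SD on day 40 (study day 41) and PD on day 88 (study day 89). The SD is too early under both counts and the PD is later than 12 weeks (84 days) under both. BOR is UNK despite two evaluable, in-window scans. With PD on day 80 instead, BOR is PD. Neither counts in DCR. Any later SD-or-better scan before progression rescues the patient. An unconfirmed PR on days 35-41 is lost in the same way if the repeat scan, at least 4 weeks later, shows PD, is unknown or is not done.

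**4. The loss can be final.** An end-of-treatment scan is required only "At the End of Treatment, if a scan was not conducted within 30 days prior to End of Treatment", and scans more than 30 days after last dose do not enter BOR (SAP 2.1.1).

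**5. Illustrative size.** The documents give no scan-timing data. Assumptions: a share e of first scans is early, spread evenly over days 35-41; second scans are spread evenly over days 77-91; PFS is exponential with survival function S; the study-day count applies; there are no other scans.

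Loss in DCR = e × [mean S(35..41) − mean S(77..91)]

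| Median PFS | mean S, first scan | mean S, second scan | Difference | Loss, e = 10% | Loss, e = 20% |
|---|---|---|---|---|---|
| 6 weeks | 0.534 | 0.251 | 0.284 | 2.8 points | 5.7 points |
| 8 weeks | 0.625 | 0.354 | 0.271 | 2.7 points | 5.4 points |
| 12 weeks | 0.731 | 0.500 | 0.231 | 2.3 points | 4.6 points |

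In a group of 20 this is 20 × 0.023 = 0.5 to 20 × 0.057 = 1.1 patients. The chance that at least one of 20 is reclassified, 1 − (1 − loss)^20, runs from 37% to 69%. For scale, the exact 90% CI for an assumed 12/20 is 39.4% to 78.3%.

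**6. The 12-week limit.** Under the study-day count, progression on an on-schedule C5D1 scan is study day 85 and falls outside 12 weeks (84 days). On elapsed days it falls inside. For a patient with no qualifying SD this decides between PD and UNK in the BOR table. It does not change DCR, because neither category counts.

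**The case against.** The strongest reply is that this is a prespecified minimum duration doing its job. A patient whose only SD scan was in week 5 has not shown SD beyond 6 weeks, the rule states what happens to such patients, and the scan window governs when scans may be done, not how long SD must last. That stands as a reason to keep the rule as the main analysis. It does not explain why two evaluable in-window scans should be reported as unknown. Appendix 1 itself allows for the assessment window when it describes the early progression rate, and Protocol 14.1.4.1 expects study-specific matters to be settled in the protocol or the analysis plan.

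Other parts of the reply also stand:

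- The size is assumed throughout. Some features reduce it: an assessment with SD "is calculated as the latest of all measurement dates (e.g. X-ray, CT-scan) if the overall lesion response at that assessment is CR/PR/SD/UNK", dose delays shift the schedule, and extra scans may rescue patients. Patients with no further evaluable scan are left out of the illustration and would add to it. The range is therefore not a bound.
- The loss is not purely a timing artefact. It is the early share multiplied by the probability of progression between the two scans, and treatment can affect the second factor.
- Individual assessments are listed by date (SAP 2.7.2), so affected patients can be identified.

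A reader might also infer that an exactly on-time C3D1 scan fails the rule. The documents do not support that. SAP 2.1.1 sets study day for all assessments and events, and on that count the scan is study day 43 and qualifies. The count is not expressly tied to BOR, and the Programming Datasets Specifications, which were not available, may settle it. The fair statement is that one sentence would remove the doubt.

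**Conclusion.** The point holds as a minor one, confined to RECIST v1.1 BOR and DCR. That days 35-41 are compliant but cannot support SD follows from the text under either day count, and the effect on DCR can only be downward.

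The size is not known. About 2-6 points, or roughly 0.5-1 patient of 20, is an illustration that depends on 10-20% early first scans, exponential PFS with a median of 6-12 weeks and none of the mitigating features above.

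A reader might go further and infer that the efficacy conclusions are biased. They are not reached by this rule: ORR does not use SD, CBR requires SD lasting about 4 months, and the expansion criteria use those same outcomes. DCR is descriptive, with an interval far wider than the illustrated loss. DCR per irRC is outside this point.

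**What to change.** By SAP amendment, or by addendum if the database is locked:

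1. Keep RECIST v1.1 BOR and DCR under the protocol rule as the main row. Add one row per group, labelled supportive, that counts SD-or-better when assessment date minus first dose date is at least 35 days, the lower edge of the scan window. All 15 compliant first-scan days then qualify.
2. Alongside it, state one day count for both BOR limits. If the SAP study-day count is used, say that the on-schedule C3D1 scan (study day 43) meets the 6-week minimum, and that progression on the on-schedule C5D1 scan (study day 85) falls outside the 12-week PD limit. The second statement affects PD versus UNK in the BOR table, not DCR.

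The cost is a sentence or two in the SAP and one extra row per group. The downside is that the supportive DCR will be the same or slightly more favourable, in an open-label study with enrolment closed. It should therefore carry the supportive label and sit below the protocol rule.
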